EduCan Trial: Study protocol for a randomized controlled trial on the effectiveness of Pain Neuroscience Education after breast cancer surgery on pain-, physical-, emotional- and work-related functioning

Trial Registration: ClinicalTrials.gov Identifier: NCT03351075

Ethical Committee of the University Hospitals Leuven: s60702

Document date: august 2024

INTRODUCTION

Breast cancer is the most frequent malignancy among women worldwide.(1) Despite the high incidence, in Western countries an increase in survival and life expectancy has been observed due to the ongoing improvement of detection method accuracy, early diagnosis, and breast cancer treatment.(1) Consequently, more attention is warranted towards the debilitating problems accompanying this disease and its treatment, which can persist for months or even years after diagnosis. In addition to fatigue, pain is the most frequent and persistent symptom following cancer and cancer treatment. Between 27 and 79% of women report pain one month after surgery, which is often attributed to local pain mechanisms caused by a post-surgery and/or radiotherapy tissue insult at that time-point. (2-5) One would expect prevalence rate to diminish as healing occurs, yet this does not seem to be the case. In fact, 12-82% of women still report persistent pain one year or later.(4) This may indicate that besides local nociceptive and neuropathic pain mechanisms, a third pain mechanism characterized by altered nociceptive processing without clear evidence of persistent tissue damage causing the activation of peripheral nociceptors (i.e. nociceptive pain) or evidence for disease or lesion of the somatosensory system causing the pain (i.e. neuropathic pain). (17-19) Moreover, pain interferes with pain-, physical-, emotional- and work-related disability and therefore severely prejudices a person's quality of life (QOL) and participation in society.(6-8) Hence, adequate pain management in the early stage of breast cancer treatment is necessary to prevent and improve pain and pain-related disability, both at short- and long-term.

Despite the effectiveness of currently applied physical therapy modalities after breast cancer surgery (such as manual techniques, specific exercises and general exercises), up to 72% of women still experience pain and the resulting disabilities after finishing breast cancer treatment.(9) Over the past decades, awareness on the important role of educational interventions in the management of cancer pain has increased.(10-12) These general educational interventions have been shown to be effective for improving pain severity, self-efficacy and knowledge and attitude to pain and analgesia in cancer patients. However, effect sizes are only moderate and of limited clinical relevance.(10) This can be explained by the fact that these educational interventions mainly focus on tissue and tissue injury as the source of

pain and are often restricted to biomedical pain management instructions and general advice on physical activity and analgesics.(10-12) They focus on explaining treatment side-effects and improving patients' coping strategies. Recently, increased knowledge on pain mechanisms has led to a more modern educational approach, also known as Pain Neuroscience Education (PNE).(13-16) This explains the neurophysiology of chronic pain and the ability of the nervous system to modulate pain experience, as well as the potential influences of sleep, thoughts, feelings and culture, among others, on pain. Thereby, it targets a reconceptualization from a biomedical or structural model to an actual biopsychosocial model of pain. Through the knowledge that pain is often an unreliable indicator of the presence or extent of tissue damage and if patients may become open to exploring broader contributions to pain, pain-related behavior might change by shifting from passive therapy-receiving to active self-management. Increased knowledge of the broad contributions to pain (4), as well as awareness of different pain mechanisms following breast cancer treatment (17-19) provides justification for the integration of PNE in this population. Applying PNE could enhance the effectiveness of the currently applied physical therapy modalities for prevention and treatment of pain and related disabilities after breast cancer treatment, compared to a traditional biomedical educational intervention. Indeed, encouraging people to address emotional, cognitive and broader health-related factors in the early stage of cancer treatment may enhance recovery during and after the treatment. To our knowledge, only one controlled trial investigated the effectiveness of PNE in the early stage of breast cancer treatment.(20) Although the results were very promising for shoulder function, only short-term effects were examined, no randomization was performed and no pain-related or other health-related outcomes were evaluated.

Objectives

The main scientific objective is to examine the effectiveness of PNE, in addition to a standard best evidence physical therapy program, on pain-, physical-, emotional-, and work-related functioning in the early stage of breast cancer treatment, compared to a traditional biomedical educational intervention, up to 1.5 years after surgery (EduCan Trial). This will be performed through a double-blinded randomized controlled trial.

METHODS AND ANALYSIS

Described according to the SPIRIT guidelines (<http://www.spirit-statement.org/protocol-version/>).

Trial design and study setting

A parallel, two-arm randomized controlled trial with blinding of assessors and physical therapists providing the standard physical therapy program in both arms and masking of the participants. The trial started in November 2017 at the department of Physical Medicine and Rehabilitation of the University Hospitals in Leuven (Belgium). A schedule of the EduCan Trial is provided in Table 1.

Table 1. Schedule of enrolment, interventions, and assessments of the EduCan Trial

	STUDY PERIOD							
	Enrolment		Allocation	Post-allocation				
TIMEPOINT	$-t_2$ preop consult	$-t_1$ postop consult	0	t_1 4 Mo	t_2 6 Mo	t_3 8 Mo	t_4 12 Mo	t_5 18 Mo
ENROLMENT								
Eligibility screen	X							
Informed consent		X						
Randomization			X					
Allocation			X					
INTERVENTIONS								
				Intensive phase	Maintenance phase			
Standard PT program (All)		n=184		1-2 sessions /week	1 session	1 session	1 session	
Pain Neuroscience Education (IG)		n=92		3 sessions	1 session	1 session	1 session	
Biomedical Education (CG)		n=92		3 sessions	1 session	1 session	1 session	
ASSESSMENTS								
Pain-related functioning (primary outcome)*	X	X		X	X	X	X	X
Pain-related outcomes*	X	X		X	X	X	X	X
Emotional functioning	X	X		X	X	X	X	X
Physical functioning*		X		X			X	X
Work-related functioning*				X	X	X	X	X

*see Table 2 for details on the content of the different assessments at each point in time

Mo = Months; IG=Intervention Group; CG=Control Group

Patient and public involvement in trial design

One female breast cancer patient and a representative of the National Health Service were consulted during the initial grant preparation and trial set up. The patient representative provided valuable insight into the worries and concerns experienced during cancer treatment. The representative of the National Health service contributed to the design of the study and advised on assessment of work-related functioning outcomes.

Eligibility criteria

Women are eligible to participate in the EduCan Trial if they are scheduled for surgery for breast cancer at the Multidisciplinary Breast Center of the University Hospitals of Leuven. Patients with increased risk of developing pain after breast cancer surgery are included.(21-23) Therefore, inclusion criteria are: 1) diagnosed with histologically confirmed invasive or non-invasive primary breast cancer, 2) scheduled for surgical excision including either axillary lymph node dissection and mastectomy (whether or not in combination with reconstructive surgery) or breast-conserving; or either sentinel node biopsy and mastectomy (whether or not in combination with reconstructive surgery); 3) aged 18 years or older; 4) can comply with the study protocol. Patients with active metastasis are excluded because of the higher risk of mortality.

[figure not shown]
Participant screening, recruitment and consent.

Participants are identified from scheduled operation lists and screened for eligibility criteria. The initial screening process is undertaken by a member of the research team. Potentially eligible participants are approached and recruited during the *preoperative consult* at the Multidisciplinary Breast Center of the University Hospitals of Leuven. All eligible patients receive an information sheet and the explanation of the study during the preoperative consult. Next, they are asked to have a preoperative baseline measurement for which a separate informed consent exists. Because of ethical and deontological reason patients will not be forced to decide on participation in the complete EduCan Trial at this moment, but initially only for the baseline measurements.

During their *postoperative hospital stay*, a member of the research team will meet the eligible participants again, answer further questions and include them in the further trial if wanted.

Then, a second informed consent is signed for participating in the complete EduCan Trial. The preoperative baseline measurement of non-participating patients will be stored in the medical file of the patient and can be consulted on clinical follow-up appointments to evaluate the recovery of the patient but is not used for research purpose. The participants' flow is summarized in Figure 1.

Figure 1: Flow diagram of the EduCan Trial

*A separate informed consent is available for the preoperative assessment
Mo=Months

Allocation and randomization

Therapists and assessors are blinded to the allocation of the treatment groups. The therapists providing the standard physical therapy program will be unaware of the type of education received by the patient (PNE in the intervention group and biomedically-focused education in the control group). Assessors are blinded to the maximal extent possible. With regard to this, patients are asked not to communicate with the assessors about the intervention

received. Patients are masked for the allocation to the intervention/control group; they do not know which one is the experimental intervention and which one is the control intervention, however they will of course be aware of the intervention received.

At the end of the trial, the success of assessor blinding will be examined by asking whether the assessor thought the participant had received the experimental or control intervention, including the percentage of certainty (i.e. 50% certainty means a pure guess). The same will be done for patient masking. The research members performing statistical analysis will be blinded as well.

The randomization is computer-generated and is performed by using permuted blocks (size=4). An independent co-worker at the department carries out the randomization to ensure blinding of the research team. The sequence of randomization is determined by the patient's identification number, which she receives after signing informed consent. Participants are randomized in a 1:1 ratio between intervention and control arms.

Interventions

Standard physical therapy program

All participants in the EduCan Trial attend a standard physical therapy program. The standard physical therapy program is based on currently available evidence and clinical experience of the research team and will include three physical therapy modalities. First, **manual techniques** including (a) passive mobilizations to restore shoulder range of motion, (b) stretching of the pectoral muscles to improve muscle flexibility and (c) scar tissue massage to improve flexibility of the scar(s) will be implemented.(9, 24, 25) Second, **specific exercises** to improve shoulder range of motion and upper limb strength have been proven to be effective for treatment of upper limb problems after breast cancer and will start immediately after surgery as well.(9, 26) Specific exercises are instructed during the individual session and continued at home. Third, patients are advised on **general exercises**. General exercises should be implemented to increase patient's physical activity level. In general, these recommendations consist of physical activity at a minimum level of moderate intensity over an extended period and can include e.g. running, walking, cycling, swimming, etc.(27, 28)

During month 1-4 an **intensive physical therapy program** is implemented because of the postoperative side-effects. Patients will attend 1-2 individual sessions of 30 minutes per week

during the intensive phase, starting one week post-surgery. All patients start with a frequency of two sessions per week, decreasing to once each two weeks. The decrease in frequency of the sessions is pragmatically chosen based on the individual progression and need of the patient.

Up to one year after surgery a **maintenance physical therapy program** is implemented to follow-up on the exercises performed at home and to treat possible additional/ new side-effects of other adjuvant treatment modalities such as radiotherapy, chemotherapy and hormone therapy. An individual maintenance session of 30 minutes is scheduled 6, 8 and 12 months post-surgery.

Additionally, **information about prevention of lymphedema** is given by a specialized physical therapist: about normal use of the upper limb, avoiding pinching off the arm, skin care and control of body weight.(29) One group information sessions of 60 minutes on this topic is organised each month which should be attended once by every participant (both patients from the intervention and control group together) and this as soon as possible after surgery. Patients also receive a brochure with this information. If patients develop lymphedema they are additionally referred to the Lymfovenous Center of the University Hospitals of Leuven for further treatment of the lymphedema.

Educational intervention

The educational sessions are individual and last for 30 minutes. The first PNE session is given within the first postoperative week before the start of the standard physical therapy program to prepare the patient for the physical therapy sessions. Information is presented verbally (explanation by the therapist) and in multi-media forms (power point presentation with summaries, pictures, metaphors and diagrams on computer). After the first session, patients also receive an information leaflet on paper and are asked to read it carefully at home. They also receive a web-link to an online presentation that summarizes the provided information. Additional written information that can be read afterwards is a valuable and essential part of the educational intervention. In the following 4 weeks after surgery, 2 additional PNE sessions are provided to ensure that the patient understands the pain physiology and principles of activity management and can relate this to the physical therapy program and his/her pain complaint. However, education is a continuous process initiated at the start and continuing

into and followed-up during the longer-term rehabilitation program. Therefore, three additional booster sessions are organized at 6, 8 and 12 months post-surgery. During the booster sessions, the information given postoperatively will be rehearsed and application of the information into future stages of the recovery process will be discussed. Special attention is given to return to preoperative activities and return to work (if applicable). Regarding this, a second information leaflet on paper will be given to the patient. Patients in the control arm and intervention arm will have the same schedule of educational sessions, only the content of the education differs from the intervention arm.

Intervention arm: Pain Neuroscience Education (PNE)

Based on the available literature a modern PNE program has been established to *explain pain* specifically for this population.(10, 12, 20) The content and pictures of the educational sessions are based on the book 'Explain Pain' (Butler & Moseley, 2003), 'Pijneducatie een praktische handleiding voor (para)medici' (Van Wilgen & Nijs, 2011) and the 'The Pain Toolkit' (Peter Moore, 2002), as used in earlier studies.(30, 31) Topics addressed during the PNE sessions will include: the characteristics of acute versus chronic pain; specific side effects of the different breast cancer treatment modalities in relation to pain; how pain is a product of the brain; how pain becomes chronic (plasticity of the nervous system, modulation, modification, central sensitization); potential sustaining factors of pain such as emotions, stress, pain cognitions, and pain behavior.

Additionally, this PNE intervention includes advice for *activity management*, while experiencing pain and other symptoms. In addition to the general recommendations for general exercise and advice to stay active in the standard physical therapy program, the PNE guides patients in performing general exercises and activities according to the graded activity principle. Graded activity is applied according to the guidelines reported by the International Association for the Study of Pain (IASP).(32) This includes general exercise activities according to pacing strategies for 'persisters' (i.e. restructuring the activity pattern to avoid peaks of over activity and exacerbations of their pain) and graded activity for 'avoiders' (i.e. time-contingent increase of physical activity). PNE is crucial here to help patients interpret pain during exercise in the correct context. Finally, advice on *returning to work* in the context of present pain complaints and how to apply the principles described above for activity management can be applied in the working situation will be provided.

Control arm: Traditional biomedical education

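### With a fixed block size of 4, up to one third of allocations are certain to anyone who learns the earlier ones, and nothing separates the staff who include women after surgery from those who deliver the education

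*Combined protocol and SAP*

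**What the plan says.** The section on allocation and randomization fixes the method in one sentence: "The randomization is computer-generated and is performed by using permuted blocks (size=4". It adds: "Participants are randomized in a 1:1 ratio between intervention and control arms". Place on the list follows the study number: "The sequence of randomization is determined by the patient's identification number, which she receives after signing informed consent". The stated safeguards are "An independent co-worker at the department carries out the randomization to ensure blinding of the research team" and "Therapists and assessors are blinded to the allocation of the treatment groups". The next sentence spells out the therapist blinding for those giving the standard physical therapy program.

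Under screening, recruitment and consent, women are first informed and approached before surgery, with a separate consent for the preoperative measurement. Entry to the trial itself comes later: "During their *postoperative hospital stay*, a member of the research team will meet the eligible participants again". The second consent is then signed. Table 1 places the eligibility screen preoperatively, one informed-consent entry postoperatively, and randomization after both.

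The educational intervention section says that a therapist gives the information in individual sessions, the first within a week of surgery, with a leaflet and a web link. Content differs by arm. The documents do not say who these educators are, whether they also recruit, or how the next allocation is hidden from the person including a woman.

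**The concern.** An independent randomizer protects the list. It does not protect against working out the next allocation from those already made. With one constant block size and a single list, each block must close at two and two, so its later places are partly or wholly determined by its earlier ones.

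Earlier allocations are known to somebody. Educators must know the arm, and they learn it within the week after surgery, while other women are being invited. If an educator also included women, or talked with the person who did, the postoperative meeting and second consent would give room to encourage, delay or not pursue a woman according to the expected arm.

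The groups could then differ at entry in distress, pain or likely adherence. The primary outcome, the PDI at 12 months, is self-reported by women who know which education they received. Such a difference could look like a treatment effect, and adjusting for preoperative PDI would remove only part of it.

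**Working it through.** The plan gives no predictability figure, so there is none to reproduce.

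**Inputs from the protocol:** block size 4 and ratio 1:1 (allocation and randomization); 184 women, so 184/4 = 46 blocks, and CV 0.5 (sample size). **Assumptions:** the probability q that an earlier allocation is known, any delay before it is known, and the alternative block sizes.

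**1. Full knowledge.** A place is certain once one arm's two places in the block are used.

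| Sequences | Certain places | Number per block |
|---|---|---|
| AABB, BBAA | 3rd and 4th | 2 |
| ABAB, ABBA, BAAB, BABA | 4th | 1 |

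Mean per block = (2×2 + 4×1)/6 = 1.333. Share = 1.333/4 = 33.3%. Over the trial, 46 × 1.333 = 61.3 of 184.

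**2. Partial knowledge.** A place is certain only if both earlier allocations that exhaust one arm are known, which has probability q². Share = q² × 1.333/4 = q²/3.

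| q | Share certain | Of 184 |
|---|---|---|
| 1 | 33.3% | 61 |
| 0.9 | 27.0% | 50 |
| 0.75 | 18.8% | 35 |
| 0.5 | 8.3% | 15 |
| 0.25 | 2.1% | 4 |
| 0 | 0% | 0 |

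**3. Delay.** If the latest allocation is not yet known, only the 4th place can be certain, and only when the first two match: (1/3)/4 = 8.3%. If the latest two are not known, the share is 0%.

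**4. Best guess.** Guessing the arm that is behind, with all earlier allocations known, succeeds with probability 1/2, 2/3, 2/3 and 1 at the four places: 2.833/4 = 70.8%, against 50% by chance.

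**5. Varying blocks of 4, 6 and 8.** In 300 simulated lists of 184, an observer who knew the set of sizes and every earlier allocation, but not each block's size, was certain of about 2%. The best guess is right 70.8%, 68.3% and 66.6% of the time in blocks of 4, 6 and 8. Weighted by block length: (4×0.708 + 6×0.683 + 8×0.666)/18 = 68.1%. A simulation of 2000 lists gave 68.0%. The gain is therefore the removal of certainty; guessing improves little.

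**6. Power of a retrospective check.** Using only the certain allocations gives about 61.3/2 ≈ 30 per direction. If CV 0.5 also holds preoperatively, the log SD is √ln(1 + 0.25) = 0.472. The difference detectable with 80% power at two-sided 5% is (1.96 + 0.84) × 0.472 × √(2/30) = 0.341 on the log scale, a ratio of 1.41. That is about 40%, twice the trial's 20% target. Including partly predictable allocations would help somewhat.

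**The case against.** The strongest reply is that no section shows a recruiter learning any allocation. The co-worker's role exists to keep the research team blind, and the person including women belongs to that team. If this works as described, the certain share is 0%. That stands, and it is why one third can only be an upper limit. What it does not answer is that educators cannot be blind to what they teach, and nothing keeps them apart from recruitment. The request for silence that women receive concerns assessors only.

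Three stronger readings are tempting and should not be made.

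- A reader might treat the inclusion criterion "can comply with the study protocol" as the means of selection, since it is a judgement. Table 1 puts eligibility screening at the preoperative consult. A woman's place on the list is not set then, because it depends on who consents in between. It is a weak lever; the exposed step is the postoperative inclusion.
- A reader might infer that the number could be issued at the first consent. The allocation section does not say which consent it means, but Table 1 largely settles it as the postoperative one. An early number would also be used up by women who later decline, whose arm is never revealed, so the certain share would fall below one third.
- A reader might say the block size was public during recruitment. The trial began in November 2017 and this document is dated August 2024, so the documents do not establish that. A constant block of 4 could still be recognized from observed allocations.

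It is also fair to object that varying blocks barely change guessing accuracy, and that enrolment may be over. Both points shape the remedy and do not remove the gap.

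**Conclusion.** The point holds as a conditional weakness with a nearly free improvement. The fixed block of 4 makes 33.3% of allocations (about 61 of 184) certain to someone who knows the block size, its boundaries and every earlier allocation in the block. The share is 19% or 8% when each earlier allocation is known with probability 0.75 or 0.5, and 0% when none is known. These probabilities are assumptions; the documents give no basis for choosing among them.

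The conclusion rests on two features of the text: a single stated block size, and the absence of any stated separation between educators and whoever includes women after surgery. A reader might infer that a third of allocations actually were foreseen, or that entry was selective. The documents support neither.

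**What to change.** **If enrolment is open:**

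- Replace the fixed size with randomly varying block sizes (for example 4, 6 and 8), known only to the independent co-worker and kept out of the protocol.
- Align the allocation section with Table 1 by stating that the number is issued after the second consent.
- State who includes women, who educates, and whether these roles are separate.

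The cost is a new list for the remaining women and a few sentences. If recruitment stops within a block, the arms could differ by at most 4 rather than 2, which is negligible at 92 per arm.

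**If enrolment is complete:**

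- Report who recruited and who delivered the education.
- Before unblinding, specify a Berger-Exner check: relate preoperative PDI, which is collected before allocation, to the allocation predicted from earlier places in the block. Use all partly predictable allocations as well as the certain ones.
- Report it beside the primary result with a note on its limited power, so that a null finding is read as weak reassurance.

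The cost is one additional analysis on data already planned.
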